#### **4.4.1 Recruitment Limitations, Anticipated Problems and Alternative Solutions**

##### **Limitations**

Some limitations or anticipated problems with recruitment may involve the efficacy of the utilized ads. In addition, participant interest may vary from population to population. There is always the possibility of restricted recruitment as it pertains to accessing and promoting studies in public spaces (i.e., schools, parks, etc.). We will also inform the study participants upon enrollment that the goal of the mLab App Plus is for self-testing and NOT for partner testing/sero-sorting. In order to ensure that DPP® HIV-Syphilis Tests are used only on the study participants themselves, participants will not be given DPP® HIV-Syphilis tests to take home. Participants will receive a test at our clinic in Washington Heights where a provider will be present and watch them self-administer the test. Because the DPP® HIV-Syphilis tests are not yet FDA approved as self-tests, it is possible that participants will be unable to perform the test on themselves, and will need the clinician to administer it for them.

##### **Alternative Solutions**

Some alternative solutions to participant recruitment may include, but are not limited to email blasts, posted flyers, and in-network recruitment. With regard to partner testing, we will suggest that participants who have partners who are interested in testing should contact the study team for more information on HIV testing. If participants are apprehensive about self-administering the DPP® HIV-Syphilis test, they will have the option to ask the clinician to administer it for them.

#### **4.5 Screening Procedures**

Interested participants will be sent a RedCap link to the mLab App Plus screener to fill out online. If found eligible, they will then have a visit at our clinic in Washington Heights with one of our investigators to answer questions and consent to enroll in the study. After receiving written consent, the study team will randomize participants to one of the two arms. After signing the consent and being randomized, they will be considered to be “enrolled” into the study.

#### **4.6 Informed Consent**

We will be using electronic online informed consent procedures for enrolling YMSM and

YTGW into the study. Interested participants will verbally consent to screening. If screened as eligible, participants will complete a consent form for enrollment into the study at the beginning of their baseline session. Prior to randomization, participants will read and sign the consent form provided to them by study staff onsite. The informed consent form provides details of the study procedure, risks, benefits, site contact information, and the nature of confidentiality and voluntary participation. The consent process also covers information on the study and compensation for time. The same consent form will be given to all study participants. Participants consent to be randomized to any of the two aims for study purposes. Before a participant signs the informed consent forms, staff will review the forms, ask if the participant understands the content of the consent forms, and answer any questions. Participants will be given a copy of the informed consent forms for their records.

## **5.0 Study Procedures**

### **5.1 Enrollment Procedures**

After successfully providing consent, the participant will be randomized to a study arm and then complete a computer self-administered baseline survey (further described in section 5.4). After completing the baseline survey, both groups will receive standard care HIV/STI testing-related risk reduction counseling, a box of condoms, and PrEP assessment. Participants who are randomized to the intervention arm will be given a DPP® HIV-Syphilis Test at their baseline appointment, which they will self-administer in the presence of a qualified clinician.

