#### **3.2 Study Randomization**

After providing informed consent, participants will be randomized to study arms in a 1:1 ratio of intervention to control arms. To reduce opportunities for selection bias, we will use a variable permuted randomization block design where block size itself is randomly selected (i.e., blocks of four to eight). The advantage of a permuted block design is that treatment assignment is pre-determined before the trial begins and assignment remains static throughout the trial. Both groups will receive standard care HIV/STI testing-related risk reduction counseling, a box of condoms, and PrEP assessment. The intervention group will self-administer their first DPP® HIV-Syphilis Test under the supervision of a trained clinician at baseline and again at their 3-month follow-up. No control group participant will be offered HIV or Syphilis testing in order to observe intervention outcome.

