##### Baseline Visit

The *baseline survey* will include questions on demographics, health literacy, sexual risk behaviors including number of men (and other genders) they engaged in anal or oral sex with, condomless anal intercourse, and HIV/STI testing history and opinions regarding HIV/STI testing. The baseline survey will also include questions on PEP/PrEP use and adherence, drug and alcohol use, and HIV Risk Index. We are using REDCAP, a web-based survey software package with several benefits that have been cited including data being captured directly in electronic format and interactive data capture checks. This approach will be especially beneficial in a multi-site study. REDCap is a secure web-based system that provides an intuitive interface, audit trails, and automated export. REDCap is a service offered through CUMC Information Technology. Staff at Columbia University will have a link to the secure web-based data collection survey tool and will be present to assist the participant in completing the survey. Staff will be accessible during survey completion to address any technical problems or to answer questions participants may have. Staff may periodically check-in with the participant to inquire about any difficulties that may arise in completing the survey. However, to ensure privacy, the staff person will not directly observe the full process of completing the survey unless requested by the participant. Both the baseline and 3-month follow up surveys will be conducted in-person.

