At the baseline study visit, following consent and completion of the baseline questionnaire, participants randomized to the intervention group will be instructed on how to use the mLab App Plus by the investigator, who will create an account for them during baseline. Next, they will verbally complete a DPP® HIV-Syphilis testing assessment so that study staff ensures they are aware of the functions and limitations of the test. Participants will be taken to the CUMC Nurse Practitioners clinic where they will be instructed to self-administer their first DPP® HIV-Syphilis test under the supervision of a trained clinician. The clinician will ensure that the DPP® HIV-Syphilis test is administered correctly and test results are accurately interpreted. The participant will use the mLab App Plus and the DPP® HIV-Syphilis testing instructions to guide them through the DPP® HIV- Syphilis testing process and to help them understand their test results. Participants will be provided with all necessary materials to complete the test by the on-site clinician. In the event that the participant feels uncomfortable or unable to perform the DPP® HIV-Syphilis test as a self-

test, they may ask the clinician to administer the test for them.

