### 3-Month Follow Up Visit

The *3-Month Follow Up* survey will include questions on demographics, health literacy sexual risk behaviors including number of men (and other genders) they engaged in anal or oral sex with, and condomless anal intercourse, as well as questions on PEP/PrEP use and adherence, drug and alcohol use, and HIV Risk Index. Participants randomized to both the control arm and intervention arm of the study will all participate in the questionnaire at the 3-month time point. The survey will also inquire about participants' opinions towards HIV/STI testing since the baseline visit and their experiences using the mLab App Plus, if they are randomized to the intervention arm.

Following completion of the survey, intervention arm participants will once again self-administer the DPP® HIV-Syphilis test at the clinic in the presence of a clinician. They will follow the same testing procedure as they did at baseline and a study team member will meet with them to discuss results and set up confirmatory testing, if necessary, once they have completed their DPP® HIV-Syphilis test. Results are stored on their smartphone through the mLab App Plus and securely transmitted and stored on the REDCap Server.

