# YMSM/YTGW attending other HIV/STI prevention service appointments
# YMSM/YTGW accessing HIV/STI prevention or social service appointments (e.g., PEP, PrEP, STI testing, mental health counseling, drug treatment, job assistance, education services, job skills training, housing assistance)
Outcome indicator data disaggregated by race/ethnicity, age, testing history and geographical area
Additional HIV-associated health outcomes (e.g., sexual behaviors associated with HIV transmission)

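### Section 5.1 puts the self-reported baseline survey after randomisation and nothing says the arm is withheld until it is submitted, so baseline self-reports could be influenced by allocation (minor)

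*Combined protocol and SAP*

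**What the plan says.** Section 5.1 (Enrollment Procedures) fixes the order at the first visit: after consent, "the participant will be randomized to a study arm and then complete a computer self-administered baseline survey". Counselling in both arms, and testing in the intervention arm, come after the survey.

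The other sections on randomisation tie it to consent and do not mention the survey. Section 3.2 has "After providing informed consent, participants will be randomized to study arms in a 1:1 ratio of intervention to control arms", section 5.3 repeats this, and section 4.5 has "After receiving written consent, the study team will randomize participants to one of the two arms".

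Under Baseline Visit in section 5.4, the survey covers demographics, health literacy, sexual risk behaviour, PEP/PrEP use, drug and alcohol use, and "HIV/STI testing history and opinions regarding HIV/STI testing". Study staff "will be present to assist the participant in completing the survey", although they do not watch the whole process unless asked. App training comes later: "following consent and completion of the baseline questionnaire, participants randomized to the intervention group will be instructed".

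The answers have three possible uses. Section 9.3.3 plans a check of baseline balance between arms. Table 2 in section 6.2 lists "Outcome indicator data disaggregated by race/ethnicity, age, testing history and geographical area", and also sexual behaviours as an additional outcome. Section 9.5 refers to a mixed model with arm, wave and their interaction, but names no outcome for it.

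**The concern.** A baseline measure is useful in a randomised comparison because allocation cannot have affected it. Here the answers are self-reported, several are sensitive or matters of opinion, and they are given after the arm has been assigned. A participant who knows that supervised self-testing is about to follow might describe past testing or views on testing differently from one who knows that only prevention links are coming. Staff who know the arm might help differently.

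If so, the answers would not be a true pre-allocation baseline. At stake are the balance check, any breakdown by survey-reported testing history, and any change or baseline-adjusted contrast on a self-report secondary measure. Section 9.2 says that the trial is meant to supply an effect size for a future RCT, so a clean baseline has some value beyond this pilot.

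**Working it through.** **1. Order of events.** Section 5.1 gives consent, randomisation, survey, counselling and testing. Sections 3.2, 4.5 and 5.3 give consent, then randomisation. They are compatible with 5.1, and none puts the survey first. Section 5.4 puts app training after the questionnaire, which delays the intervention but does not say that the arm is unknown during the survey. No section describes blinding, masking or delayed disclosure. Items answered in the online eligibility screener (sections 4.1 and 4.5) precede randomisation and are not exposed.

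**2. What is exposed.** The primary outcome (section 6.2) is judged by the supervising clinician and has no survey baseline. The one comparison named in the Data Analysis Plan (section 9.4) is a logistic regression of testing on arm, with no baseline term stated. Neither depends on the survey order. The uses that do are the balance check (9.3.3), the breakdown by testing history where it is taken from the survey (Table 2), and, conditionally, an arm-by-wave or baseline-adjusted analysis of a self-report measure (Table 2 and 9.5).

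**3. Bias formulas.** The plan gives no figure for a reporting shift, so there is nothing to reproduce. Let the intervention arm's reports shift by b0 at baseline and b1 at 3 months, with no true effect, unit SD and baseline-to-3-month correlation rho:

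- change contrast: b1 − b0
- baseline-adjusted contrast: b1 − rho × b0
- unadjusted 3-month contrast: b1

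**4. Numbers.** From the documents: 40 participants, 1:1, so 20 per arm. Assumed for illustration: a shift of 0.1 to 0.3 SD, rho of 0.5 to 0.7, a normal measure, complete follow-up. At 0.3 SD, with rejection rates of a nominal 5% two-sided test from simulation (40,000 replicates):

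| Pattern | Change | Baseline-adjusted | 3-month only |
|---|---|---|---|
| Shift at baseline only | −0.30 SD; 15–22% | −0.15 to −0.21 SD; 8–14% | 0; 5% |
| Same shift at both visits, survey after randomisation | 0; 5% | +0.09 to +0.15 SD; 6–8% | +0.30 SD; 15% |
| Shift at 3 months only (the row above with a clean baseline) | +0.30 SD; 15–23% | +0.30 SD; 18–25% | +0.30 SD; 15% |

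The adjusted column follows from the formulas: −0.5 × 0.3 = −0.15 and −0.7 × 0.3 = −0.21 in the first row; (1 − 0.7) × 0.3 = 0.09 and (1 − 0.5) × 0.3 = 0.15 in the second. For a baseline-only shift of 0.1 or 0.2 SD, the change contrast rejects 6–7% or 10–12% of the time.

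**5. Could the planned balance check catch it?** The SE of a baseline difference is √(2/20) = 0.316 SD. The 95% half-width is 2.024 × 0.316 = 0.64 SD. A two-sample t-test flags a shift of 0.1, 0.2 or 0.3 SD about 6%, 10% or 15% of the time, and cannot separate it from chance imbalance.

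**6. Against sampling error.** The SE of the change contrast is √(2(1 − rho) × 2/20): 0.316 at rho 0.5 and 0.245 at rho 0.7. The half-widths are 0.64 and 0.50 SD. Every bias in the table is smaller than these.

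**The case against.** The best reply is that being randomised is not the same as being told. The protocol never says that the arm is disclosed before the survey; the survey is computer self-administered and mostly unobserved; and everything specific to an arm comes afterwards. This stands as a limit on the claim. A reader might infer that participants answer knowing their arm, or that the baseline data are biased. The documents support neither. They show only that the order permits it and that nothing prevents it.

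A second reply is that no analysis with a named outcome is damaged. That is largely right. A reader might extend the concern to the primary outcome or to the testing comparison, but neither uses the survey baseline. The model in section 9.5 names no outcome, so that consequence is conditional.

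A third reply is that moving the survey can make some contrasts worse, and this also stands. At 3 months the survey asks intervention participants about "their experiences using the mLab App Plus, if they are randomized to the intervention arm", so they know their arm by then. If reporting shifts equally at both visits, the current order cancels the shift in a change contrast and reduces it in an adjusted one. A clean baseline exposes it in full (second and third rows of the table). That is not a reason to keep a baseline that may be contaminated, because the cancellation requires equal shifts at the two visits, which nobody can verify. It does mean that reordering must not be presented as removing reporting bias.

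**Conclusion.** The point holds as a minor weakness of design. The order in section 5.1 is explicit, and no safeguard is stated. Baseline self-reports could be influenced by allocation, and the planned balance check would rarely show it (about 15% of the time at an assumed 0.3 SD).

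The size and direction of any shift are unknown, and the 0.1 to 0.3 SD range, the correlations, normality and full follow-up are all assumptions. Under them a baseline-only shift biases a change contrast by the whole shift with opposite sign, and an adjusted contrast by rho times that. Both are smaller than the sampling error of a 40-person trial. A change would be worthwhile because it is nearly free, not because a main result is at risk.

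**What to change.** In section 5.1, have the baseline REDCap survey submitted after consent and before randomisation, at the same visit; then release the allocation and go on to counselling and the arm-specific procedures. Alternatively, keep the order and state that the arm is withheld from participants and survey staff until submission.

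The cost is about one sentence in 5.1, with the same visit, staff and survey. Sections 3.2 and 5.3 remain true as written. So does the definition of enrolled in section 4.5, because consent and randomisation are both still required.

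Add a line to the analysis section saying that this protects only the baseline, and that differences in self-reported measures at 3 months are to be interpreted as unblinded.

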### 1.3 Rationale

In response to the mLab App study and the scientific evidence of need for at-home syphilis POC testing among YMSM and YTGW, we propose to implement the **mLab App Plus** to assess YMSM's and YTGW's abilities to perform and interpret self-tests for HIV and syphilis and consequently increase the number of YMSM and YTGW who initiate self-testing for HIV and syphilis.

We propose the following Specific Aims:

- 1: Examine the feasibility of using the DPP® HIV-Syphilis test as a self-test to improve uptake and access to STI testing.
- 2: Estimate the effect sizes for the mLab App Plus for improving testing uptake in YMSM and YTGW.

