**Table 1. Schedule of Events**

	Intervention Arm		Control Arm	
	Baseline	3-Months	Baseline	3-Months
Standard-of-Care Counseling a	X		X	
Online Survey	X	X	X	X
mLab App Plus	X			
DPP® HIV-Syphilis Test	X	X		

a: Receipt of standard-of-care HIV/STI testing-related risk reduction counseling, box of condoms, PrEP assessment, and referral information for clinics that provide PrEP.

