#### **9.4 Data Analysis Plan**

All multivariate analyses will be preceded by standard descriptive bivariate analyses to describe the key variables and relationships among them. These analyses will include means, frequency tables, histograms, and examination of distributions. Frequencies and rates of HIV/syphilis tests, as well as corresponding confidence intervals, will be calculated for each arm (mLab App Plus vs. Standard of Care (Control)). Logistic regression models will be used to compare in the likelihood of having HIV/STI tests between the mLab App Plus arm and the standard clinic-based testing arm.

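### Randomisation precedes the testing counselling and PrEP assessment that both arms should receive alike, so their delivery can differ by arm and affect the Aim 2 uptake comparison

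*Combined protocol and SAP*

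**What the plan says.** Section 5.1 fixes the order of the baseline visit: "After successfully providing consent, the participant will be randomized to a study arm and then complete a computer self-administered baseline survey". The common package comes next: "After completing the baseline survey, both groups will receive standard care HIV/STI testing-related risk reduction counseling", along with condoms and a PrEP assessment. Under Section 4.5, "the study team will randomize participants to one of the two arms". The documents describe no masking of staff or participants.

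Table 1 marks one counselling package at baseline for both arms. Its footnote defines the package as "Receipt of standard-of-care HIV/STI testing-related risk reduction counseling, box of condoms, PrEP assessment, and referral information for clinics that provide PrEP". Sections 3.2 and 5.3 both carry a study-wide rule: "No control group participant will be offered HIV or Syphilis testing in order to observe intervention outcome".

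Aim 2 in Section 1.3 reads "Estimate the effect sizes for the mLab App Plus for improving testing uptake in YMSM and YTGW". Section 9.4 gives the matching analysis: "Logistic regression models will be used to compare in the likelihood of having HIV/STI tests" between the two arms.

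**The concern.** The counselling and PrEP assessment are meant to be a constant, the same for everyone, so that a difference between arms can be credited to the app and self-test. Under the Section 5.1 order they are given once the arm can be known. The subject of the counselling is also the behaviour being compared. A counsellor who knows that a participant is a control might say less about testing, because the study offers that person none. The same counsellor might instead say more, to make up for it. Either would be performance bias in the Aim 2 effect size, which Section 9.2 says is wanted for a future trial.

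This is separate from any effect of allocation on baseline survey answers. Moving only the survey ahead of randomisation would still leave the counselling after it.

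**Working it through.** The documents give no uptake rate, and Section 9.2 states n=40 without a power, alpha or effect size. There is therefore no planned figure to reproduce, and the check is mainly a reading of the sections against each other.

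1. **Order.** Section 5.1 gives consent, then randomisation, survey, counselling and PrEP assessment. Sections 3.2, 4.5 and 5.3 also place randomisation directly after consent. No section puts the counselling before allocation.

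2. **Knowledge of arm.** The study team randomises at the visit (4.5), and no masking is described. The documents do not say which staff member counsels, so it is possible, but not stated, that the counsellor knows the arm.

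3. **Link to outcome.** The counselling is about testing (3.2, 5.1, Table 1), and Section 9.4 compares having tests. The PrEP assessment bears on the Table 2 row that counts access to services, which includes PrEP and STI testing.

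4. **Reason to differ.** Counselling on testing is given to controls under a rule that they are offered no test. No section says what a control may be told about being tested elsewhere.

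5. **Safeguards.** The documents describe no counselling script, fidelity check or delivery log. Data Monitoring (9.3.3) covers protocol compliance in general, baseline balance and attrition. None of these compares counselling by arm.

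6. **Outcomes exposed.** The primary outcome in Section 6.2 is successful self-administration of the DPP test. Table 1 gives that test to the intervention arm only, so the primary outcome is not affected. For tests done in the clinic, the arms already differ by design: one arm is tested at both visits and the other is not. Uneven counselling can therefore matter mainly for tests obtained outside the study, and for the service-access counts. Section 9.4 does not say which tests count.

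7. **What can be said about size.** Suppose uneven counselling moves uptake by dI in the intervention arm and dC in the control arm. Then:

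   observed difference = true difference + dI − dC

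   Each point of unequal shift moves the estimate by one point. The documents give neither dI nor dC. Any difference in delivery that follows the arm is also confounded with the arm, so the data could not separate it at any sample size. Precision does not help either. With 40/2 = 20 per arm, the widest 95% half-width for a risk difference (both rates at 50%) is

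   1.96 × √(0.25/20 + 0.25/20) = 1.96 × √0.025 = 0.31

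   A modest shift would be well inside that margin.

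**The case against.** The strongest reply is that this is an open-label feasibility pilot, and giving a common standard-care package after allocation is a defensible choice. Intervention participants also receive app instruction, a verbal assessment of their understanding of the test, supervised testing, a discussion of results and app reminders (5.4, 8.2). Re-ordering one session leaves all of that in place. This stands, and it limits what the change can achieve. It does not remove the reason to protect the one component that the protocol describes as the same in both arms.

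A reader might infer that the counsellors are themselves barred from discussing testing with controls, or that counselling is planned to differ. The documents support neither. They do not name the counsellor, and the rule concerns offering a test, not giving information. Section 3.1 has controls sent testing and PrEP information by email, and Table 1 gives one package for both arms.

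A reader might also want to attach a sample-size consequence. Suppose uptake of 45% against 20%, and n per arm = (1.96 + 0.84)² × [p1(1 − p1) + p2(1 − p2)]/(p1 − p2)². A future trial then needs about 51 per arm, and moving control uptake to 25% or 15% changes that to about 85 or 33. Both the rates and the shift are invented, and they do not fit the planned comparison. The intervention arm is tested in the clinic at both visits, and Table 2 counts testing at those visits, so its uptake should be near the ceiling. At an assumed 95% against 20%, the same formula gives 7.84 × 0.2075/0.5625, or about 3 per arm. An illustration that depends this heavily on an assumed rate should not be used to size the problem.

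**Conclusion.** The point holds as a weakness in procedure. A package meant to be identical in both arms, and aimed at the Aim 2 outcome, is delivered when the arm can be known, with nothing described to keep delivery equal. It rests on the order in Section 5.1 and on the absence of any described masking or standardisation. It does not rest on evidence that counselling will differ.

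Its reach is limited to the between-arm uptake comparison, chiefly tests obtained outside the study, and the secondary service-access counts. Neither size nor direction can be derived from the documents. It is a cheap improvement worth making, not an error that threatens the trial's main purpose.

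**What to change.** In Section 5.1, order the baseline visit as follows:

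1. Consent.
2. Baseline survey.
3. The common package: counselling, condoms, PrEP assessment and referral information.
4. Randomisation, with the arm revealed only at this step.
5. App instruction and the DPP test (intervention), or the email of online information (control).

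Align the wording of Sections 3.2, 4.5 and 5.3, and keep the next assignment hidden from the counsellor until step 4. Consent still precedes randomisation (4.6), and app instruction and testing still follow the questionnaire (5.4). Make the change together with moving the survey ahead of allocation, since one re-ordering does both. The content of the package, the visit and the staff stay the same.

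The cost is a wording change and some survey and counselling time for anyone who leaves before allocation. Under Section 4.5 such a person would not yet count as enrolled. The change does not remove arm-dependent contact after allocation. If the order cannot be changed, a scripted and logged session, with a written rule on what controls may be told about testing elsewhere, would be a weaker substitute.
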